4.6.4. Additional Safety Assessments

4.6.4.1. Central Laboratory Measures and Vital Signs

Summary tables will be presented for clinical laboratory tests with numeric values for participants in the Safety set. Observed results at each visit will be presented.

Summary tables presenting observed values and changes from baseline (for those parameters which are measured post-baseline) will be presented for clinical laboratory tests with numeric values for participants in the Safety set. Changes from baseline to each scheduled post-baseline visit will be presented.

A listing of abnormal findings will be created for laboratory analyte measurements. The listing will include patient ID, laboratory collection date, study day, analyte name, and analyte finding.

For clinical chemistry, the following laboratory tests will be included:

Sodium, Potassium, Chloride, Bicarbonate, Total bilirubin, Direct bilirubin, Alkaline phosphatase (ALP), Alanine aminotransferase (ALT), Aspartate aminotransferase (AST), Gamma-glutamyl transferase (GGT), Blood urea nitrogen (BUN), Creatinine, Creatine kinase (CK), Uric acid, Total protein, Albumin, Calcium, Phosphorus, Glucose.

All chemistry data by participant will be presented in a listing.

For hematology, the following laboratory tests will be included:

Hemoglobin, Hematocrit, Erythrocyte count (RBCs - red blood cells), Mean cell volume, Mean cell hemoglobin, Mean cell hemoglobin concentration, Leukocytes (WBCs - white blood cells), Differential (Neutrophils, Lymphocytes, Monocytes, Eosinophils, Basophils, Platelets, Cell morphology (RBCs and WBCs) if indicated.

All hematology data by participant will be presented in a listing.

For lipid panel, the following laboratory tests will be included:

Total cholesterol, Triglycerides, High-density lipoprotein (HDL-C), Low-density lipoprotein (LDL-C), Very low-density lipoprotein (VLDL-C).

All lipid panel data will be presented in a listing.

As for urine chemistry, the following tests will be included:

Albumin, Creatinine

All urine chemistry data will be presented in a listing.

Additional tests:

Calcitonin

All additional tests will be presented in a listing.

Calculations:

Urinary albumin/creatinine ratio (UACR), eGFR (CKD-EPI) calculated using creatinine. All calculations will be listed.

Laboratory Tests for Hepatic Evaluation

- Hepatic Hematology Panel: Hemoglobin, Hematocrit, Erythrocytes (RBCs - red blood cells), Leukocytes (WBCs white blood cells), Differential (Neutrophils, segmented Lymphocytes, Monocytes, Basophils, Eosinophils, Platelets, Cell morphology (RBC and WBC).
- Hepatic Clinical Chemistry Panel: Total bilirubin, Direct bilirubin, Alkaline phosphatase (ALP), Alanine aminotransferase (ALT), Aspartate aminotransferase (AST), Gamma-glutamyl transferase (GGT), Creatine kinase (CK)
- Hepatic Coagulation Panel: Prothrombin time, INR (PT-INR)
- Urine Chemistry: Drug screen
- Haptoglobin
- Hepatitis A virus (HAV) testing: HAV total antibody, HAV IgM antibody
- Hepatitis B virus (HBV) testing: Hepatitis B surface antigen (HBsAg), Hepatitis B surface antibody (anti-HBs), Hepatitis B core total antibody (anti-HBc), Hepatitis B core IgM antibody, HBV DNA
- Hepatitis C virus (HCV) testing: HCV antibody, HCV RNA
- Hepatitis D virus (HDV) testing: HDV antibody

- Hepatitis E virus (HEV) testing: HEV IgG antibody, HEV IgM antibody, HEV RNA
- Anti-nuclear antibody (ANA)
- Anti-smooth muscle antibody (ASMA)
- Anti-actin antibody
- Epstein-Barr virus (EBV) testing: EBV antibody

Laboratory assessments will be performed by a central laboratory. All summaries will be based on the units provided by the central laboratory, no conversion will be done.

All relevant clinical laboratory tests will be classified as treatment emergent Low, Normal, and High, or Normal/Abnormal according to the normal ranges. This categorical data will be summarized in shift tables comparing the results at each scheduled post-baseline visit with those at the baseline visit. The percentages of participants with treatment-emergent abnormal, high, or low laboratory measures at each post-baseline visit will be summarized.

When there are multiple values within a visit for a particular laboratory variable, the worst value will be taken (worst being the smallest value for criteria below a certain threshold or the largest value for criteria above a certain threshold). If a participant has a value below the threshold and above the threshold, the value furthest from the threshold will be chosen.

A treatment-emergent abnormal value is defined as a change from normal value at baseline to an abnormal value at any time during the follow-up.

Definition of treatment emergent Low/High results:

- A treatment-emergent high result is defined as a change from a value less than or equal to the high limit at baseline to a value greater than the high limit at any time during the Treatment and Follow-up periods.
- A treatment-emergent low result is defined as a change from a value greater than or equal to the low limit at baseline to a value less than the low limit at any time during the Treatment and Follow-up periods.
 - Laboratory normal ranges will be provided by the Central Lab.

An MMRM using REML model will be used to analyze the changes in lipid panel parameters from baseline to all scheduled post-baseline visits. The model will include visits and baseline HbA1c category ($\leq 8.0\%$, >8.0%) as fixed effects and baseline value of the dependent variable as a covariate.

Vital signs:

Summary tables presenting observed values and changes from baseline will be presented for vital sign data, *systolic blood pressure (mmHg), diastolic blood pressure (mmHg), pulse rate (bpm),* weight (kg), Waist Circumference measurement (cm) and BMI for participants in the Safety set. For height (cm), only observed values will be summarized at baseline.

Height and weight measurements will be used to calculate BMI, with following formula:

 $BMI = weight (kg) / [height (m)]^2$

Descriptive summaries by nominal visit will be provided for baseline and postbaseline values as well as change from baseline values. If 2 records are taken at the same visit, they will be averaged prior to being used for data summaries and analyses.

An MMRM using REML model will be used to analyze the changes in vital signs from baseline to all scheduled post-baseline visits. The model will include visits and baseline HbA1c category ($\leq 8.0\%$, >8.0%) as fixed effects and baseline value of the dependent variable as a covariate.

Counts and percentages of patients with treatment-emergent abnormal sitting systolic blood pressure (BP), sitting diastolic BP, and pulse will be presented. The criteria for identifying patients with treatment-emergent vital sign abnormalities are stated in Table 4.

Table 4.Categorical Criteria for Abnormal Treatment-Emergent Blood Pressure and
Pulse Measurement

Parameter	Low	High
Systolic BP (mm Hg) (Supine or sitting – forearm at heart level)	Observed value ≤ 90 and decrease from baseline ≥ 20	Observed value ≥ 140 and increase from baseline ≥ 20
Diastolic BP (mm Hg) (Supine or sitting – forearm at heart level)	Observed value ≤ 50 and decrease from baseline ≥ 10	Observed value ≥ 90 and increase from baseline ≥ 10
Pulse (bpm) (Supine or sitting)	Observed value ≤ 50 and decrease from baseline ≥ 15	Observed value ≥ 100 and increase from baseline ≥ 15

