### 9.3.5.3. Central Laboratory Measures and Vital Signs

Values and changes from baseline to postbaseline values of appropriate central laboratory measures and vital signs will be summarized at each scheduled visit.

The analysis model to make comparisons within treatment relative to continuous change from baseline values assessed over time will be an MMRM, with terms: visit, country, and baseline measurement as covariates.

An unstructured covariance structure will model relationship of within-participant errors.

The percentages of participants with treatment-emergent abnormal, high, or low laboratory measures at any time will be summarized.

A treatment-emergent abnormal value is defined as a change from normal value at baseline to an abnormal value at any time during the follow-up.

A treatment-emergent high result is defined as a change from a value less than or equal to the high limit at baseline to a value greater than the high limit at any time during the Treatment and Follow-Up periods.

A treatment-emergent low result is defined as a change from a value greater than or equal to the low limit at baseline to a value less than the low limit at any time during the Treatment and Follow-Up periods.

High and low limits will be provided in SAP.

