4.1. General Considerations

Statistical analysis of this study will be the responsibility of Lilly or its designee.

Any change to the data analysis methods described in the protocol will require an amendment *only if* it changes a principal feature of the protocol. Any other change to the data analysis methods described in the protocol, and the justification for making the change, will be described in the statistical analysis plan or clinical study report. Additional exploratory analyses of the data will be conducted as deemed appropriate.

Nominal significance levels:

All tests of treatment effects will be conducted at a 2-sided alpha level of 0.05, unless otherwise stated, and all confidence intervals will be given at a 2-sided 95% level.

Timing of Primary Analysis:

Primary analysis will be performed at database release after Last Participant Last Visit (LPLV).

Definition of baseline:

Baseline is defined as the last non-missing measurement recorded on or before the date/time of first dose. If the measurement time is not specified, it is assumed that any measurement taken on the date of first dose occurred prior to dosing.

Populations for analysis:

- Analyses will use the EAS to evaluate the primary efficacy estimand for all (secondary and exploratory) endpoints.
- Safety analysis will be performed on the SS.

Pooling of data:

Study data will be pooled across centers.

Analysis Windows:

Visit windows will be defined for by-visit summary and analysis purposes. Summary data such as adverse events and concomitant medications which are not reported by visit will not use visit windows. Visit labels will be assigned to each post-baseline record based on the windows or intervals for study day relative to the date of first dose. A record with the study day closest to the target visit day (week \times 7 days + 1) will be chosen when multiple records fall in the same visit window. In case of a tie, the record with the earlier date will be chosen. If Day 1 is missing, the closest visit on or before the date of first dose will be used as baseline. All visits will be included in the summary tables for worst post-baseline values.

All efficacy and safety analyses will be based on the visit windows in Table 1.

Study Day Relative to First Dose	Visit	Target Day
Study day ≤ 1	Baseline	1
$2 \leq study \ day \leq 43$	Week 4 (Visit 3)	29
$44 \leq \text{study day} \leq 81$	Week 8 (Visit 4)	57
$82 \leq study \ day \leq 88$	Week 12 (Visit 5)	85

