4.9. Changes to Protocol-Planned Analyses

There are no changes to protocol planned analyses.

5. Sample Size Determination

A sample size of 150 participants will provide at least 90% power to show an improvement in HbA1c from baseline at Week 12. This sample size is using the following assumptions:

- a 1-sample t-test with 2-sided significance level of 0.05
- within treatment difference from baseline at Week 12 is 0.3%, and
- intra-subject variability of 1.1%.

6. Supporting Documentation

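### The protocol promises an any-time percentage for treatment-emergent laboratory abnormalities; the SAP specifies only by-visit percentages and declares no change

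*SAP*

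**What the plan says.** Protocol 9.3.5.3 makes this commitment: "The percentages of participants with treatment-emergent abnormal, high, or low laboratory measures at any time will be summarized".

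SAP 4.6.4.1 uses nearly the same sentence with a different ending: "The percentages of participants with treatment-emergent abnormal, high, or low laboratory measures at each post-baseline visit will be summarized". The definitions in that section stay any-time. An abnormal result is "a change from normal value at baseline to an abnormal value at any time during the follow-up", and a high result is a change from at or below the limit at baseline "to a value greater than the high limit at any time during the Treatment and Follow-up periods". The low definition mirrors the high one.

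SAP 4.9 states: "There are no changes to protocol planned analyses". SAP section 1 says the same.

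Three other provisions decide where a value lands:

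- SAP 4.1: "Visit labels will be assigned to each post-baseline record based on the windows or intervals". Table 1 sets Week 4 as Days 2–43, Week 8 as Days 44–81 and Week 12 as Days 82–88.
- SAP 4.6.4.1: "When there are multiple values within a visit for a particular laboratory variable, the worst value will be taken". SAP 4.1 has a different general rule for several records in one window: "A record with the study day closest to the target visit day" is chosen.
- SAP 4.1 sets the default percentage denominator as everyone in the analysis set, unless stated otherwise.

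**The concern.** The event is defined over the whole treatment period but reported in slices. For most chemistry analytes and for lipids the slices are very uneven. The Schedule of Activities (Protocol 1.3) plans those samples after baseline only at Visit 5 and at the ED visit, so the Week 4 and Week 8 rows can hold only ED and unscheduled samples. The Week 12 row is the only one with a planned sample behind it, and it is the one a reader will naturally take as the rate.

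At stake is a descriptive safety percentage that the protocol promised. It covers analytes such as creatinine and electrolytes, which bear on two of the protocol's safety topics of special interest, dehydration and renal safety (8.3.3.2 and 8.3.3.3). Both the protocol (9.3.1) and the SAP (4.1) require a change of analysis method to be described and justified in the SAP or study report. The SAP describes none here.

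**Working it through.** The documents state no figure on this point, so there is nothing to reproduce. The check is a trace through Table 1, followed by an illustration with assumed rates.

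**Trace.** A value on Day 30 goes to the Week 4 row, on Day 60 to Week 8, and on Day 85 to Week 12. A value on Day 89 or later has no window. Windows run without a gap from Day 2 to Day 88, so ED and unscheduled values in that span are assigned to some row. If the worst-value rule applies, an abnormal one is kept there. No row combines the windows.

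**Illustration (all rates assumed).** N = 150; 10% leave the study before Day 82 and give an ED sample (15 leavers, 135 completers); 20% of leavers and 8% of completers have a treatment-emergent high value.

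- Any-time: (15 × 0.20 + 135 × 0.08)/150 = (3 + 10.8)/150 = 9.2%.
- Week 12 row, full-set denominator: 10.8/150 = 7.2%. Ratio 9.2/7.2 = 1.28.
- Week 4 and Week 8 rows together: 3/150 = 2.0%. The rows sum to 7.2% + 2.0% = 9.2%.

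| Leavers | Any-time | Week 12 row | Ratio |
|---|---|---|---|
| 5% | (7.5 × 0.20 + 142.5 × 0.08)/150 = 8.6% | 11.4/150 = 7.6% | 1.13 |
| 10% | 9.2% | 7.2% | 1.28 |
| 15% | (22.5 × 0.20 + 127.5 × 0.08)/150 = 9.8% | 10.2/150 = 6.8% | 1.44 |

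These ratios compare the Week 12 row alone with the any-time rate. If leavers have the same 8% risk as completers, the any-time rate is 8.0% and the Week 12 row is still 7.2%, because leavers stay in the denominator while their ED values sit in other rows.

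**Why adding rows does not recover the rate.** Suppose 2% of completers (2.7) also have an abnormal unscheduled value before Day 82, one each. The Week 4 and Week 8 rows then total (3 + 2.7)/150 = 3.8%, Week 12 is 7.2%, and the sum is 11.0%. If those 2.7 are among the 10.8 abnormal at Week 12, the true any-time rate is 9.2% and the sum double counts. If they were abnormal only early, the true rate is (3 + 2.7 + 10.8)/150 = 11.0%. The same rows fit both.

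**Wider range.** Take 5% of completers abnormal at Week 12, 5–15% leaving, 5–40% of leavers abnormal, and 0–5% of completers abnormal only before Day 82. The any-time rate runs from 5.0% to 14.5%, the Week 12 row from 4.25% to 4.75% of the Safety Set. The top is (0.15 × 0.40) + (0.85 × 0.10) = 14.5%, with every assumption at its extreme.

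**The case against.** The strongest reply is that almost nothing is lost, and most of it stands.

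- A reader might infer that early stoppers and unscheduled values drop out of the reported rate. The documents do not support that. Windowing places values through Day 88 in some row, and the laboratory worst-value rule retains the abnormal ones. Participants who stop tirzepatide are to remain in the study and attend the remaining visits (Protocol 7.1), and their data stay in the Safety Analysis Set. Only those who leave the study, which Protocol 7.2 expects to be uncommon, miss the Week 12 sample.
- A reader might also infer that the SAP's rate is biased downward as a whole. In the first illustration the rows sum exactly to 9.2%. The shortfall appears only when the Week 12 row is read alone, and the SAP names no headline rate. Nothing in the documents shows that leavers have more abnormalities.
- Values after Day 88 are marginal. Visit 5 is allowed ±3 days, which is Days 82–88, and no later visit is scheduled.
- Other outputs give partial cover. SAP 4.6.4.6 plans maximum post-baseline shift tables for ALT, AST and bilirubin and a baseline to post-baseline shift table for alkaline phosphatase, including unplanned measurements. Abnormal findings are listed, and clinically relevant laboratory changes are to be reported as adverse events (Protocol 8.2.5). Hematology, urinalysis and calcitonin are scheduled at screening only.
- Table specifications sit in a separate document, and SAP 4.1 mentions worst post-baseline tables, so an any-time table may exist there.

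The last point does not settle the matter. SAP 4.6.4.1 specifies no such table for general laboratory tests, a listing is not a rate, and the SAP text is what departs from the protocol.

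**Conclusion.** The mismatch is real and undeclared: any-time in the protocol and in the SAP's definitions, by-visit in the SAP's planned summary. For laboratory tests outside SAP 4.6.4.6, mainly non-liver chemistry and lipids, following the SAP as written gives no percentage that counts each participant once. The Week 12 row understates that percentage when study leavers or transient abnormalities fall in earlier windows, and the sum of rows can overstate it.

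The size rests wholly on assumed leaver and abnormality rates. With few leavers and few transient abnormalities the gap is small, and that is the likely case. A further uncertainty is which within-window rule applies. If the closest-to-target rule in SAP 4.1 were used for laboratory tests, some abnormal unscheduled values would be lost from the percentages.

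Severity is low to moderate. This is descriptive safety output with no bearing on the primary analysis or any hypothesis test, but it is wrong as written and easy to correct.

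**What to change.** In SAP 4.6.4.1:

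1. Add one any-time post-baseline percentage per analyte and direction. Count each participant once and use all scheduled, ED and unscheduled treatment-period values regardless of Table 1 windows.
2. State the denominator, for example Safety Set participants not already abnormal in that direction at baseline with at least one post-baseline value.
3. Keep the by-visit percentages and shift tables as supportive.
4. State that the worst-value rule in 4.6.4.1 overrides the closest-to-target rule in 4.1 for these laboratory categories.

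With the any-time percentage restored, the no-change statements in SAP 1 and 4.9 can stand on this point. If the sponsor prefers by-visit reporting only, 4.9 should declare and justify it.

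The cost is about one sentence and one extra table. The reported percentage may be slightly higher than the Week 12 row.

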# 8.2.5. Clinical Safety Laboratory Tests

See Section 10.2, Appendix 2 for the list of Clinical Laboratory Tests to be performed and the SoA (Section 1.3) for the timing and frequency.

The investigator must review the laboratory results, document this review, and report any clinically relevant changes occurring during the study as an AE.

The laboratory results must be retained with source documents unless a Source Document Agreement or comparable document cites an electronic location that accommodates the expected retention duration.

Clinically significant abnormal laboratory findings are those which are not associated with the underlying disease, unless judged by the investigator to be more severe than expected for the participant's condition.

All laboratory tests with values considered clinically significantly abnormal during participation in the study should be repeated until the values return to normal or baseline or are no longer considered clinically significant by the investigator or medical monitor.

- If such values do not return to normal or baseline within a period of time judged reasonable by the investigator, the etiology should be identified, and the sponsor notified.
- All protocol-required laboratory assessments, as defined in Section 10.2, Appendix 2, must be conducted in accordance with the SoA (Section 1.3), standard collection requirements, and laboratory manual.

If laboratory values from non-protocol-specified laboratory assessments performed at an investigator-designated local laboratory require a change in participant management or are considered clinically significant by the investigator, for example, SAE or AE or dose modification, then report the information as an AE.

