# 8.2.7. Hepatic Monitoring

#### **Close hepatic monitoring**

#### Initiating laboratory and clinical monitoring for abnormal liver laboratory test results

Laboratory tests, including ALT, AST, ALP, TBL, direct bilirubin, GGT, and creatine kinase, should be repeated within 48 to 72 hours to confirm the abnormality and to determine if it is increasing or decreasing, if 1 or more of these conditions occur. This table shows if a repeat laboratory test is needed.

If a participant with baseline results of	develops the following elevations
ALT or AST <1.5x ULN	ALT or AST ≥3x ULN
ALP <1.5x ULN	ALP ≥2x ULN
TBL <1.5x ULN	TBL ≥2x ULN (except for participants with Gilbert's syndrome)
ALT or AST ≥1.5x ULN	ALT or AST $\geq 2x$ baseline
ALP ≥1.5x ULN	$ALP \ge 2x$ baseline
TDI >1.5 v LII N	TBL ≥1.5x baseline (except for participants with Gilbert's
$1DL \ge 1.3X$ ULIN	syndrome)

Abbreviations: ALP = alkaline phosphatase; ALT = alanine aminotransferase; AST = aspartate aminotransferase; TBL = total bilirubin level; ULN = upper limit of normal.

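### SAP 4.6.4.1: if a laboratory test is both low and high within one visit, the tie-break can drop one treatment-emergent event from the by-visit counts, and the worst-value rule is not reconciled with SAP 4.1 (minor)

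*SAP*

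**What the plan says.** SAP 4.6.4.1 (Central Laboratory Measures and Vital Signs) starts with a general rule: "When there are multiple values within a visit for a particular laboratory variable, the worst value will be taken". In parentheses it makes worst direction-specific: the minimum for criteria that look below a limit, the maximum for criteria that look above one. The next sentence is the tie-break: "If a participant has a value below the threshold and above the threshold, the value furthest from the threshold will be chosen".

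The paragraph just before it names the outputs. They are shift tables by scheduled visit and this summary: "The percentages of participants with treatment-emergent abnormal, high, or low laboratory measures at each post-baseline visit will be summarized". The definitions that follow treat the two directions separately. For low: "A treatment-emergent low result is defined as a change from a value greater than or equal to the low limit at baseline" and then "to a value less than the low limit at any time during the Treatment and Follow-up periods". The definition for high mirrors it.

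SAP 4.1 (Analysis Windows) assigns every post-baseline record to a Table 1 window. The record nearest the target day "will be chosen when multiple records fall in the same visit window", and the earlier date wins a tie. SAP 4.1 applies these windows to all efficacy and safety analyses. Its one exemption covers summary tables of worst post-baseline values.

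**The concern.** There are two problems in the same paragraph.

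First, the tie-break undoes the direction-specific rule before it. Low and high are separate events with separate percentages, so nothing requires choosing between them. Keeping one value means a participant who meets both definitions in a window is counted for one. Which one is counted depends on a distance that the SAP does not define.

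Second, the worst-value rule and the closest-day rule both claim the by-visit shift tables and percentages, and neither is said to take precedence. The difference matters most where a repeat follows an abnormal result, because closest-day selection can then put the normal repeat in place of the abnormal value.

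At stake is the accuracy and reproducibility of a few entries in the by-visit laboratory safety tables. Two programmers could follow the SAP faithfully and produce different counts.

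**Working it through.** The plan states no figure on this point, so there is nothing to reproduce. The check applies each rule to small examples. Their limits and values are assumptions, not trial data.

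**1. One set of records, three readings.** Assume limits of 3.5 to 5.3, a normal baseline, and three values in the Week 12 window (Days 82 to 88, target Day 85): 3.2 on Day 83, 4.4 on Day 85 and 5.9 on Day 88.

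- Tie-break: the distances are 3.5 − 3.2 = 0.3 and 5.9 − 5.3 = 0.6, so 5.9 is kept. High is counted and low is not.
- Closest day (SAP 4.1): the distances from Day 85 are 2, 0 and 3, so 4.4 is kept. Neither is counted.
- Each definition applied separately: the minimum 3.2 is below 3.5 and the maximum 5.9 is above 5.3. Both are counted.

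**2. No distance scale.** Assume limits of 70 and 100 and values of 52 and 125.

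- Absolute distance: 70 − 52 = 18 against 125 − 100 = 25. This keeps 125.
- Relative distance: 18/70 = 25.7% against 25/100 = 25.0%. This keeps 52.

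The unstated scale decides whether the low is counted.

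**3. Literal reading with one threshold.** The sentence uses the singular. Take one upper limit of 40 and values of 10 and 45. The distances are 30 and 5, so 10 is kept. That value is not elevated, which contradicts taking the worst.

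**4. Where several values can arise.** In the Schedule of Activities, chemistry and lipids have one scheduled on-treatment sample after baseline (Visit 5, or the early-discontinuation visit). Hematology is at screening only. The Table 1 windows span 43 − 2 + 1 = 42, 81 − 44 + 1 = 38 and 88 − 82 + 1 = 7 days, but the two long ones contain no scheduled chemistry. Multiple values therefore need extra samples, and the protocol provides for three kinds:

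- Clinically significant abnormal results "should be repeated until the values return to normal or baseline" (Protocol 8.2.5), or until no longer considered clinically significant.
- Liver-related tests that meet the monitoring triggers "should be repeated within 48 to 72 hours to confirm the abnormality" (Protocol 8.2.7).
- A sample from a non-fasting attendance is kept and a fasting one is rescheduled (Protocol 1.3).

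**5. Can closest-day selection pick the repeat?** Take Visit 5 on each of Days 82 to 88 with a repeat 2 or 3 days later, which gives 7 × 2 = 14 combinations.

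- Day 82 is 3 days from target; its repeats on Days 84 and 85 are 1 and 0 days away. The repeat is chosen.
- Day 83 is 2 days away; its repeats on Days 85 and 86 are 0 and 1 days away. The repeat is chosen.
- Day 84 is 1 day away; its repeats on Days 86 and 87 are 1 (tie, earlier record kept) and 2 days away. The first sample is kept.
- On Days 85 to 88 the first sample is nearer.

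The repeat is chosen in 4 of 14 combinations. This shows that the rules can diverge. It is not a probability: the lag comes from the hepatic rule alone, and Protocol 8.2.5 gives no interval.

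**The case against.** The strongest reply is that the remedy is largely in the text already. The parenthetical gives minimum for low and maximum for high, and the tie-break can be read as serving only the shift table, where one participant needs one cell. On that reading the separate definitions still count both events. This is a fair reading, but the SAP does not limit the sentence in that way. The sentence follows directly after the paragraph that specifies the percentages as well as the shift tables.

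On the conflict with SAP 4.1, a specific laboratory rule would ordinarily prevail over a general one. The same section also gives vital signs a rule of their own, namely averaging. That is the natural resolution. It is not stated, however, and SAP 4.1 lists an exemption that leaves these by-visit tables out.

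The objection on reach stands. Abnormal values are listed, and chemistry data are listed in full. When both limits are crossed, the retained value is itself abnormal, so the combined abnormal count does not change. ALT, AST, bilirubin and alkaline phosphatase have separate shift tables in SAP 4.6.4.6 that include unplanned samples, with maximum values specified for all but alkaline phosphatase in the table description. Repeats taken after Visit 5 may lie outside the Safety Analysis Set: SAP 3 restricts it to treatment-period data, and SAP 1.2 ends that period at Visit 5.

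A reader might also infer that the worst value enters the continuous summaries and the lipid MMRM. The documents do not support that. The rule speaks of criteria and a threshold, and neither continuous analysis refers to worst values. A reader might further infer that glucose will often be both low and high in a window, given the population. No second chemistry sample is scheduled in any window, and hypoglycemia has its own collection and analysis (Protocol 8.3.3.6, SAP 4.6.4.2).

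**Conclusion.** The point holds and is minor. As written, the tie-break can remove a low or a high that meets the SAP's own treatment-emergent definition from the by-visit percentages, and it cannot be programmed in only one way. The unreconciled rules in SAP 4.6.4.1 and SAP 4.1 can make the same shift entry abnormal or normal.

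The conclusion rests on two readings: that the tie-break governs the percentages as well as the shift tables, and that a visit means the Table 1 window, as SAP 4.1's labelling implies. Only participants with a repeat, rescheduled fasting or unscheduled sample in a window can be affected. The documents do not allow their number to be estimated. It would be wrong to conclude that abnormal values vanish from the trial record, or that any efficacy result is affected.

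**What to change.** In SAP 4.6.4.1:

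- Delete the furthest-value sentence for the treatment-emergent percentages. Judge low on the minimum and high on the maximum of all values in the window, independently, so that both can count.
- In the shift tables, use one low-direction and one high-direction entry.
- State that this rule overrides the closest-day rule of SAP 4.1 only for shift tables and treatment-emergent percentages. Continuous summaries and the lipid MMRM keep the SAP 4.1 record. Add the matching exemption to SAP 4.1.

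The cost is a few sentences in the SAP, minor programming, and a second shift entry for the rare participant with values in both directions. No data collection changes.
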